- e. Is there a location dependent EMG response to capsaicin induced sensitization? In other words, do the texture features or EMG responses from muscles that lie anatomically distant from the location of the site of intramuscular capsaicin injection have changes from their baseline calculations? This would test the hypothesis that type III and IV afferents have an influence on the anterior horn cells that lie distant to the ones that are supplying muscle fibers in the vicinity of the stimulated sensory afferents.
- f. Is there a dose dependent EMG response of motor units to capsaicin induced sensitization? Here, the hypothesis of causality will be assessed in a preliminary manner. If there is a relationship then further experiments that more thoroughly assess causality will be needed.

Methods & Design

Study Design:

The study conforms to the Consolidated Standards of Reporting Trials recommendations.

Ethical approval is approved by the University Health Network (UHN) Research Ethics Board.

This study is registered under the National Institutes of Health ClinicalTrials.gov.

This proposed study is a single centered, factorial, randomized placebo-controlled trial with two independent variables, depth of capsaicin application and dose of capsaicin, for a total of nine treatment arms. The first between groups variable will be topical capsaicin application

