and injectable capsaicin injection. Within each partition there will be three treatments: control, 50 micrograms, 100 micrograms. One-hundred micrograms reported to be an effective high dose of capsaicin.[13] The control group will receive a topical skin lotion which is inert and has no sensitization effect. An equal number of participants will be allocated to each of the six treatment groups using an electronic randomization generator. Block randomization will be used to ensure equal allotment into each group. An alternate member of the research team will conduct the randomization schedule a priori. Participant allocation will be concealed by placing their assignment in an envelope and delivered to participants by the same member of the research team uninvolved in the measurement or randomization protocols. Participants and investigators will be blinded to the delivered dose; however, the type of capsaicin delivery cannot be blinded from either participants or investigators. The member of the research team conducting the randomization schedule and concealing allocation will have knowledge of and keep track of the doses contained in the containers and vials of the topical and injectable capsaicin, respectively. They will deliver the appropriate dose to the team member implementing the experimental protocol to ensure there is blinding with respect to dose. This individual will not be involved in participant recruitment.

Participants

Recruitment

Participants will be recruited from UHN and the University of Toronto clinics, employees, volunteers, visitors, students, and external participants. UHN is a tertiary healthcare centre with eight hospitals located in Toronto, Canada and the University of Toronto is an academic institution with a main campus located in close proximity to the main UHN hospitals

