Capsaicin will be applied directly to the region of the innervation zone at the muscle belly to sensitize the neurons within the region of taut band development. Topical and intramuscular capsaicin will be used. The capsaicin formula will be compounded by a registered pharmacist. Topical capsaicin will be delivered in a cream and injectable capsaicin will be intermixed with saline prior to injection. The control group in the topical capsaicin arm will be treated with the cream base used during the experiment without added capsaicin and the injection arm will be injected with saline. A trained medical professional on the research team will apply the topical capsaicin or topical placebo treatments. The region of topical application will measure 5cm squared in the dermatome zone location to cover an area of approximately 25cm². A trained physician in physical medicine and rehabilitation will deliver injectable capsaicin using a 27-gauge needle at the location of the superior fascia of the upper trapezius muscle with ultrasound guidance. The fascial layer was chosen as it is the region with the lowest pressure pain threshold relative to skin and muscle, suggesting a high density of nociceptors within the layer, and it possesses connections to the spinal cord.[27] Changes in muscle fascia properties and nociception at muscle fascia, compared to nociception at muscle or subcutaneous tissue, has also been implicated in the development of pain.[28,29] Furthermore, intramuscular capsaicin will also be injected using ultrasound guidance to avoid the superior or inferior fascia.

To confirm the presence of central sensitization, brush allodynia will be used to detect mechanical hyperalgesia outside the region of primary nociception—region of topical placement or injection—which is the region of secondary hyperalgesia.[13-15] The size of the region of secondary hyperalgesia will be measured to characterize the extent of central sensitization. This will be accomplished using a tape measure and the perpendicular dimensions of the region of secondary hyperalgesia will be recorded in square centimeters.

Ultrasound analysis

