texture features will be computed in MATLAB and principal component analysis will be computed to reduce the variables. A repeated measures MANOVA will be applied for each intervention group. To test the change in EMG within and between groups a repeated measurement ANOVA will be applied considering each intervention group as a factor. The dependent variable would be considered as pain intensity, duration, and area of pain in separate analysis. Data distributions would be first checked with the Shapiro-Wilk to conform the normal distribution of the data. Additionally, we will test for the homogeneity of variance using Mauchly's test as well as correcting the degrees of freedom if necessary [40]. If the assumption of normality not met, for all skewed data an appropriate transformation will be used. We will construct univariate and multivariable linear regression models of differences in EMG amplitude (differences between after and before) as a function of intervention groups when adjusted for important covariates. Due to small sample size in each group, there is not possible to adjust for several covariates. Therefore, in a univariate model we will find the most important ones. For initial selection of relevant variables, all variables with a p-value ≤ 0.2 in the univariate analysis will be selected and retained in the multivariable analysis.

All Statistical analyses will be conducted with SAS for Windows (version 9.3; SAS Institute, Inc, Cary, NC). Using a two-sided test a P-value ≤ 0.05 will be considered as statistically significant.

Discussion

This will be the first study that assesses the effect of capsaicin induced central sensitization on ultrasound texture features and muscle motor unit activity. Findings from this

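### EMG is analysed only by intervention group, so the plan names no test of research question (f), dose dependence

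*Combined protocol and SAP*

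**What the plan says.** **Design.** The Study Design section specifies "two independent variables, depth of capsaicin application and dose of capsaicin, for a total of nine treatment arms". It continues: "Within each partition there will be three treatments: control, 50 micrograms, 100 micrograms". On allocation: "An equal number of participants will be allocated to each of the six treatment groups". The section on inducing central sensitization gives each route its own control: the topical control receives the "cream base used during the experiment without added capsaicin and the injection arm will be injected with saline". Route is open: "the type of capsaicin delivery cannot be blinded from either participants or investigators".

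**Question.** Research question (f) reads: "Is there a dose dependent EMG response of motor units to capsaicin induced sensitization". The text below it treats the answer as a preliminary look at causality.

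**Analysis.** For EMG change within and between groups, "a repeated measurement ANOVA will be applied considering each intervention group as a factor". A linear regression of before-to-after EMG amplitude change also takes intervention group as its explanatory variable, with covariates. The Statistical analysis plan mentions no dose term, route term, interaction, trend, planned contrast or post-hoc comparison. The sample size is likewise built on a single set of seven groups measured twice.

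**The concern.** The randomised structure separates two things: how the substance is delivered and how much capsaicin it contains. The analysis as written merges them into one unordered list of groups.

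An overall group-by-time test asks only whether any group's change differs from any other's. It takes no account of dose order. It also responds to anything that distinguishes an injection from a cream, including the procedure itself and participants' knowledge of the route. A significant result therefore would not show that EMG depends on dose, or that capsaicin did anything. A non-significant result could hide a dose trend spread over 5 degrees of freedom.

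EMG recruitment and amplitude are a primary outcome, and (f) is the question through which causality is to be explored. If no dose test is named beforehand, one will have to be chosen after the data are seen, across many EMG parameters.

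**Working it through.** **1. The plan's own figure.** The sample size section gives a minimum of 70 for 7 groups and 2 measurements, with effect size 0.5, correlation 0.5, alpha 0.05 and 80% power. I take g = 0.5 as f = 0.25 and test the group-by-time interaction with noncentrality (N − 7) × 2 × 0.25² / (1 − 0.5) = 0.25(N − 7). This gives N = 68, or 70 when balanced over 7 groups. With N in place of N − 7 the answer is 62 (63 balanced). So 70 is reproduced under one convention, for an undivided group-by-time test. The target of 84 is 70 × 1.2.

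**2. Set-up for the check.**
- Layout: 2 routes × 3 dose levels, six equal arms (Study Design).
- SD of change = SD × √(2(1 − 0.5)) = SD, from the plan's correlation of 0.5.
- n per arm: 10 (70/7), 12 (84/7) or 14 (84/6), shown as a range because the arm count is not settled.
- The 0.5 SD effect borrows the plan's generic effect size. The 0.75 SD effect is my assumption, since the documents give no EMG SD or expected route difference.
- Two-sided alpha 0.05; error df = 6n − 6.

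**3. Formulas** (D = effect in SD units; power from the noncentral F).
- Overall group test, 5 df: λ = n Σ(μᵢ − μ̄)².
- Dose trend averaged over route, 1 df, weights (−1, 0, 1): λ = n × (mean at 100 µg − mean at control)².

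**4. Route difference only, no capsaicin effect.** Three arms sit at 0 and three at D, so λ = n × 6 × (D/2)² = 1.5nD². For n = 12 and D = 0.75, λ = 10.125.

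| n per arm | Overall test significant, D = 0.5 | D = 0.75 |
|---|---|---|
| 10 | 24.9% | 54.1% |
| 12 | 30.2% | 64.1% |
| 14 | 35.5% | 72.6% |

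In 20,000 simulated trials at n = 12 and D = 0.5, the overall test rejected in 30.2%. Once route was a separate factor, the dose test rejected in 4.9%, in line with its nominal 5%.

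**5. Linear dose effect, equal in both routes.** Means are 0, D/2, D in each route, so λ = nD² for every test that contains the dose effect. Only the degrees of freedom differ. For n = 12 and D = 0.75, λ = 6.75.

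| n per arm | D | Overall, 5 df | Dose, 2 df | Trend, 1 df |
|---|---|---|---|---|
| 12 | 0.5 | 20.6% | 30.9% | 40.0% |
| 12 | 0.75 | 44.8% | 61.7% | 72.6% |
| 14 | 0.5 | 24.0% | 35.7% | 45.5% |
| 14 | 0.75 | 52.3% | 69.2% | 79.1% |

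**6. Where the gain disappears** (n = 14, D = 0.75).
- *Effect in the injection arms only* (0, D/2, D there; 0 in all topical arms). The route-averaged difference halves to 0.375, so the trend has λ = 14 × 0.375² = 1.97 and power 28%. The overall test has λ = 6.89 and power 46%, but 2.95 of that λ is the difference between route means. The contrast of 100 µg with control within injection has λ = 14 × 0.75²/2 = 3.94 and power 50%.
- *Full response at 50 µg and half at 100 µg, both routes.* Trend 28%, overall test 52%, 2-df dose test 69%.

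**The case against.** Four points can fairly be made for the plan.

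**The wording is loose.** A reader might infer that the plan cannot answer (f) at all. That goes too far. If the regression codes group with indicator variables, dose contrasts can be computed from it, and the design section does name two independent variables. What stands is that no such contrast is specified.

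**A route difference is a true finding.** A reader might call a route-driven result a false positive. It is not: route is a randomised variable of interest, and rejecting equality of all groups is then correct. Nor does the plan say it will read the overall test as a capsaicin or dose effect. What stands is that the overall test cannot serve as the answer to (f), and it is the only group comparison named.

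**The power gain is conditional.** A reader might infer that the flat analysis roughly halves power in general. Step 6 of the working shows otherwise, and the plan studies route because the routes may respond differently.

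**The trial is exploratory.** Question (f) is the last of six and is called preliminary, with further experiments foreseen. This lowers the severity. It does not remove the need to say which test addresses a listed question when a significance threshold of 0.05 is in use.

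**Conclusion.** The point holds as a gap between design and analysis: a route-by-dose factorial and an explicit dose question, but EMG models that refer only to intervention group. That gap does not depend on any assumed effect size.

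The size of the consequence does depend on assumptions: six equal arms, change-score SD equal to outcome SD, and effect sizes the documents do not supply for EMG. Under these, the group test is significant from route alone in 25 to 36% of trials at 0.5 SD and 54 to 73% at 0.75 SD, over 10 to 14 per arm. The trend's advantage (40% against 21% at 0.5 SD with 12 per arm) further requires a linear dose effect that is equal in both routes.

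Severity: should-fix. The documents do not support saying that (f) is unanswerable, that the group test has an inflated error rate, or that the sponsor intends to claim dose dependence from it.

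**What to change.** **First reconcile two matters on which the model depends.**
- *The arms.* The Abstract gives four treatment arms plus two controls. Study Design gives nine arms and then six groups. The sample size uses seven. The Experimental Protocol lists a fascial injection followed by an intramuscular one and names no saline control, while Study Design describes the control only as a topical lotion.
- *The withdrawal rule.* The section on determination of central sensitization withdraws subjects who are not sensitized after a second application. It does not say whether this covers controls. If it does, few zero-dose participants may remain and dose comparisons would be hard to interpret.

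**Then amend the Statistical analysis plan.**
- Model EMG change on route, dose and route-by-dose.
- Name the dose test averaged over route as the test for (f): the 1-df trend, shown with the 2-df dose test.
- Report the route-by-dose term, and the capsaicin-minus-control contrasts within each route with 95% CIs.
- State that the overall group test will not be read as evidence of a capsaicin or dose effect.

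**Cost.** No new data are needed. The model is a change of wording, but reconciling the arms is more than that. The pooled trend loses power when slopes differ between routes or the response is non-linear, which is why the 2-df test and the within-route contrasts are shown beside it.

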in Toronto. Advertisements, flyers, and in person recruitment will be employed to collect the necessary sample size for the study. The recruitment procedures will run in line with the approved guidelines from the UHN research ethics boards. Participants will not be coerced into participating and will be informed that they have the right to withdraw at any time during the experimental procedures. They will also be informed they have the right to withdraw their data prior to publication. Participants will be briefed and consented on recruitment prior to commencing the study procedures. Participant treatment allocation will be recorded on a separate document until all of the data collection is complete and the data is analyzed.

Eligibility Criteria

Female or male participants who meet the following inclusion criteria will be included in the study: (1) participants are healthy with no past medical history (2) a visual analogue score below 3 indicating low pain severity, however, ideally who complain of no pain (3) right or left handed, (4) normal body mass index, (5) have sufficient command of the English language to provide informed consent and to understand the study protocols, (6) participants agree to sign a consent to volunteer for the research.

Exclusion Criteria

Participants who meet one or more of the following criteria will be excluded: (1) history of pain, (2) physical examination detection of myofascial trigger points, (3) participants present with a history of pain related disturbances such as poor sleep, cognitive disturbances, psychiatric disorders, (4) history of general medical disorder that may affect the outcome of the study such as diabetes mellitus, (5) and a history of cervical radiculopathies or (6) history of inflammatory arthropathy.

Experimental Protocol

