The Delsys Trigno system, which includes sensors, the Trigno base station, and the EMGworks software will be used to decompose the acquired EMG signals into individual motor units. The following parameters will be analyzed: the firing times and frequency of individual motor units, motor unit action potential amplitude and shapes[36-38], the root mean square value (RMS) of each channel and of the entire signal[16], the coefficient of variation for force steadiness[39], and the centroid of the EMG signal in the cranial-caudal and the medial-lateral directions[16]. This will be repeated for each contraction.

Intramuscular EMG analysis

A 27g monopolar electromyography needle will be placed into the midbelly of the upper fibers of the trapezius muscle using ultrasound guidance. The intramuscular EMG signals will be measured using Cadwell Sierra Wave. Since this system does not offer motor unit decomposition, we will use the intramuscular EMG analysis to provide us with more details of the gross EMG measurements such as the overall RMS value, the coefficient of variation for force steadiness, and the centroid measurements.

Determination of Central Sensitization:

Before measuring outcomes, approximately 20 minutes after capsaicin application we will analyze the area of secondary hyperalgesia for each study subject, then determine whether central sensitization has in fact been induced. The presence of central sensitization is confirmed by expansion of the receptive field and area of secondary hyperalgesia beyond the 25 cm² initial application area. If it has, the study participant will undergo the rest of the experimental methodology. If it has not, the capsaicin will be applied once more and the region of secondary hyperalgesia will be remeasured in 20 minutes later. The above described process for confirming the presence of central sensitization will take place again. If the study participant has not had sensitization at this stage they will be withdrawn from the study.

Primary Outcomes

The primary outcome measures:

1. Textural regional changes
2. Recruitment and Amplitude regional changes

These will be recorded for each arm of the study, please see figure 1.

Secondary outcomes:

1. A record of adverse events

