2. Safety evaluation The investigating physician monitors the patient clinically for signs of distress. The methods and timing for assessing, recording, and analyzing safety parameters. Any signs of distress noted by investigating physician will be assessed clinically and appropriately managed. The information will be recorded on the patient's data form. The study team will discuss all incidents and any potential causal link to the study interventions. Patients will be provided with a contact number for the principal

investigator in order to report any changes that occur during or after the study. Our publication will include a list of any adverse events or intercurrent illness encountered. Any patient who experiences an adverse event will be triaged to their family physician or local emergency department as necessary. They will be contacted after to obtain information on the course of their treatment and the outcome of the event.

3. Sample size calculation.

Using GPower V3.0.10 (Dusseldorf, Germany), considering a medium effect size (Hedge's G) of 0.5 and a moderate correlation coefficients (0.5) among repeated measures, sample size calculation determined that a minimum of 70 participants would be required to detect differences via repeated measures ANOVA (two measurement as before and after among 7 groups) with 80% power and an alpha of 0.05. We aim to recruit 84 participants to account for potential attrition (~20%) of participants given the study duration and frequency of follow-up visits.

We plan to recruit equal number of men and women. To date, there are no reported sex differences in induction of Central Sensitization using Capsaicin among males and females with neurological impairments.

4. Statistical analysis plan

Baseline participants' characteristics including demographics will be analyzed using appropriate descriptive statistics. Mean and standard deviation will be calculated for continuous variables. Categorical variables will be presented as numbers and percentages. To test the change in ultrasound images from baseline to experimental conditions, the

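### The ANOVA announced for EMG change is given pain measures as its dependent variables, and recruitment, one of the two parts of primary outcome 2, has no named test and no defined measure

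*Combined protocol and SAP*

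**What the plan says.** Primary outcome 2 is "Recruitment and Amplitude regional changes" (Primary Outcomes). The secondary outcomes are adverse events and a safety evaluation. Research question d, in the Background, concerns recruitment of motor units.

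Section 4 (Statistical analysis plan) treats EMG in three steps:

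- It announces the test: "To test the change in EMG within and between groups a repeated measurement ANOVA will be applied", with intervention group as a factor.
- The next sentence reads: "The dependent variable would be considered as pain intensity, duration, and area of pain in separate analysis".
- Later it adds univariate and multivariable "linear regression models of differences in EMG amplitude", the difference being after minus before, with intervention group as predictor.

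Section 3 (Sample size calculation) uses the same kind of design: a minimum of 70 participants is "required to detect differences via repeated measures ANOVA (two measurement as before and after among 7 groups". It names no outcome.

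On pain, Eligibility Criteria requires "a visual analogue score below 3 indicating low pain severity". Under Inducing central sensitization, "The size of the region of secondary hyperalgesia will be measured to characterize the extent of central sensitization". Under Determination of Central Sensitization, that area is assessed about 20 minutes after application and decides who continues; after a second failed attempt, "If the study participant has not had sensitization at this stage they will be withdrawn from the study".

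**The concern.** The sentence on the dependent variable directly follows the EMG ANOVA and is the only one in the plan that says what an ANOVA's dependent variable is. Taken as written, the test introduced for EMG is run on three pain variables that are not trial outcomes.

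At stake is the recruitment half of primary outcome 2. No stated test names it, and no section says which quantity represents it. An analyst would have to choose both the measure and the way of summarising it, possibly with the data in hand, and then judge the result at P ≤ 0.05. Question d would have no endpoint fixed in advance.

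**Working it through.** No figure of the plan is disputed here, so the check sets the sections side by side and adds one algebraic step.

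**1. What is listed, measured and tested (visible text).**

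| Quantity | Listed outcome? | Measured after capsaicin? | Named in a stated test? |
|---|---|---|---|
| Pain intensity | No | None scheduled; only the eligibility score | ANOVA |
| Pain duration | No | None scheduled | ANOVA |
| Area of pain | No | Nearest is area of secondary hyperalgesia, with no described value before application | ANOVA |
| EMG amplitude | Primary outcome 2 | Yes | Regression on the difference |
| Recruitment | Primary outcome 2 | Raw data yes, derived measure no | None |

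Of the three dependent variables given to the ANOVA, none is a listed outcome. Of the two components of primary outcome 2, one is named in a model.

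**2. Is amplitude left untested?** No. Let D be a participant's after-minus-before difference, with k groups and N participants. In a repeated-measures ANOVA with two time points:

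- SS(group × time) = ½ Σ n_g (D̄_g − D̄)², on k − 1 degrees of freedom
- SS(error) = ½ ΣΣ (D_gi − D̄_g)², on N − k degrees of freedom

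The factor ½ cancels in the F ratio. What remains is the one-way ANOVA of D on group, which is the overall group test in a regression of D on group indicators. With the 7 groups and 70 participants of section 3, both have 7 − 1 = 6 and 70 − 7 = 63 degrees of freedom. The unadjusted amplitude regression therefore delivers the test that the ANOVA would have delivered for amplitude. The identity does not depend on the number of groups, and it does not extend to the covariate-adjusted model.

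**3. Is recruitment tested?** There are two readings.

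- *Literal:* the ANOVA analyses pain, the regression analyses amplitude, and recruitment has no test.
- *Generous:* the pain sentence adds further analyses. The EMG ANOVA then has no named dependent variable, and recruitment is included only because it is a kind of EMG change.

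**4. Is recruitment defined?** The raw material is planned: a force-tracked ramp to 30% of maximal voluntary contraction (Experimental Protocol), a baseline recruitment curve (Measurement of motor unit activity using EMG), and firing times from each contraction (sEMG Analysis). No parameter of the curve is named. The sEMG list offers several candidates (firing times, firing frequency, potential amplitude and shape, RMS, force steadiness, centroid), and recruitment is not among them.

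**5. Is there one value per participant and time?** Four contractions are made before and four after, each yielding individual motor units. No rule reduces them to the single before and single after value that a two-measurement ANOVA needs. This gap affects amplitude as much as recruitment. The side is also open: the load cell is attached to one arm (Experimental Protocol), whereas EMG is taken on both sides (sEMG Analysis).

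**6. Minor.** Section 4 assigns homogeneity of variance to Mauchly's test. That test concerns sphericity. With two time points there is 2 − 1 = 1 within-participant contrast, so sphericity holds trivially, and the test says nothing about variances between groups.

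**The case against.** The strongest reply is that the literal reading is the less natural one. The purpose clause says the ANOVA is for EMG, and the reference to separate analysis may mean that pain is analysed in addition. The trial calls itself exploratory, firing times and frequency are among the parameters to be analysed, and amplitude has its own model.

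Much of this stands. The generous reading is quite possible, and the amplitude point is correct. But that reading moves the gap without closing it, because the EMG ANOVA then has no named dependent variable and recruitment still has no measure. The exploratory label does not remove the need for a definition when the plan declares primary outcomes, a power calculation and a significance threshold.

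A reader might also infer more than the documents support:

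- *That primary outcome 2 is not tested at all.* Amplitude is tested by the regression on the difference; only recruitment is affected.
- *That pain is never rated after capsaicin.* Figure 2, the protocol timeline, is not shown and could contain such a rating. The statement covers the visible text only.
- *That two-sided EMG doubles the four force-tracked ramps at each time point.* Only one arm is attached to the load cell, so the text supports four.
- *That the sample size is thereby wrong.* Section 3 names no outcome, and nothing in this point bears on the figure of 70.

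**Conclusion.** The point holds and should be corrected before analysis: the sentence on the dependent variable is wrong as written for an ANOVA meant to test EMG change. Its reach is one of the two components of primary outcome 2. On the literal reading, recruitment has no test; on the generous reading, it has a generic test with an open measure. Amplitude is tested on either reading, though its summary over units and contractions is also unstated.

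This rests on three conditions: the visible text without Figures 1 and 2, two time points as in section 3, and, for the equivalence, the unadjusted regression with group as a categorical factor. The wording conflict is certain. Which of the two readings was intended cannot be settled from the documents.

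**What to change.** Replace the pain sentence in section 4 with: *The dependent variables of this ANOVA are motor unit action potential amplitude and motor unit recruitment; the test of interest is group × time.*

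Then, before any EMG data are examined:

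- Fix one recruitment measure from data already planned. One example is load-cell force, as a percentage of maximal voluntary contraction, at each decomposed unit's first firing on the rising ramp.
- State one rule, for amplitude and recruitment alike, that reduces units and the four contractions to one value per participant before and one after.
- State the side and region analysed, and reconcile the one-arm load cell with the two-sided EMG.
- List pain intensity and duration as exploratory if they are measured; otherwise delete them. Report the area of secondary hyperalgesia separately as a manipulation check.
- Check homogeneity of variance with the Levene or Brown-Forsythe test on change scores.

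The cost is plan wording and one endpoint definition. No new recordings are needed, since force and firing times are already planned, and sample size, alpha and the ANOVA are unchanged.
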